### **5.4.11 Plasma levels – Baclofen, Methadone, Growth Hormone**

Plasma concentrations of baclofen, methadone and growth hormone will be measured from whole blood. Blood samples of up to 10ml will be obtained at baseline and 1, 2, 3, 5 hours after dosing, in total a maximum of 50ml blood.

### **5.4.12 Adverse events**

Emergence of side effects of baclofen will be assessed as appropriate and recorded according to the MedDra dictionary.

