#### **5.4.3 Baclofen or Placebo Dosing & Administration**

The dose recommendation from the model will be administered approximately 1 hour after methadone. The dose levels are 10mg, 30mg, 60mg or 90mg, administered as either 1, 3, 6 or 9 tablets of baclofen respectively, or a matching number of placebo (vitamin D) tablets which are a very close visual match (see section 5.7).

Effects of baclofen or placebo will be monitored for up to 5 hours following dosing at the Clinical Research Facility. Any lasting effects will be monitored at a follow-up telephone call the following day.

Placebo or baclofen tablets will be administered with water by a nurse or study team member under direct supervision. Participants will not be given the chance to scrutinise the contents of the medication pot prior to consumption. This is a single-blind trial, therefore the participants will not be aware of whether they are taking placebo or baclofen tablets.

NB Baclofen reaches peak maximum concentrations approximately 1-2 hours after oral dosing with 60mg ( $C_{max}$ ; 88-102 minutes, (Durant et al., 2018), and has an estimated half-life in plasma of ~3 hours after a single 60mg dose (range = 2.7-3h from 10-90mg baclofen). All testing will therefore be covered by baclofen's pharmacokinetic profile.

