### **5.7.4 Emergency Unblinding Procedure**

This is single-blind- study clinicians and researchers will be aware of the drug allocation that was recommended by the adaptive trial algorithm and this allocation will be stored within the OpenClinica Database and accessible to the research team.

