#### **8.3.6 Adverse events**

Adverse events will be tabulated by treatment group (baclofen versus placebo). Where useful a time to event analyses will be undertaken to depict the timing of adverse events (using hazard plots) and display the difference in time to event curves between treatment groups (baclofen versus placebo) and baclofen dose group for comparative purpose.

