#### **10.1.2 CAUSALITY**

Most adverse events and adverse drug reactions that occur in this study, whether they are serious or not, will be expected treatment-related toxicities due to the drugs used in this study. The assignment of the causality should be made by the investigator responsible for the care of the participant using the definitions in the table below.

If any doubt about the causality exists the local investigator should inform the study coordination centre who will notify the Chief Investigators. The pharmaceutical companies and/or other clinicians may be asked to advise in some cases.

In the case of discrepant views on causality between the investigator and others, all parties will discuss the case. In the event that no agreement is made, the MHRA will be informed of both points of view.

Relationship	Description
Unrelated	There is no evidence of any causal relationship
Unlikely	There is little evidence to suggest there is a causal relationship (e.g. the event did not occur within a reasonable time after administration of the trial medication). There is another reasonable explanation for the event (e.g. the participant's clinical condition, other concomitant treatment).
Possible	There is some evidence to suggest a causal relationship (e.g. because the event occurs within a reasonable time after administration of the trial medication). However, the influence of other factors may have contributed to the event (e.g. the participant's clinical condition, other concomitant treatments).

Probable	There is evidence to suggest a causal relationship and the influence of other factors is unlikely.
Definitely	There is clear evidence to suggest a causal relationship and other possible contributing factors can be ruled out.
Not assessable	There is insufficient or incomplete evidence to make a clinical judgement of the causal relationship.

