### **10.1.3 REPORTING PROCEDURES**

All adverse events should be reported. Depending on the nature of the event the reporting procedures below should be followed. Any questions concerning adverse event reporting should be directed to the study coordination centre in the first instance. A flowchart is given below to aid in the reporting procedures.

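### Section 5.4.12 frames visit-day adverse-event capture around baclofen and leaves it to unblinded staff without a standard question, so the descriptive baclofen-versus-placebo adverse-event comparison is open to detection bias

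*Combined protocol and SAP*

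**What the plan says.** Section 5.4.12 is the procedure paragraph for adverse events at the experimental visit: "Emergence of side effects of baclofen will be assessed as appropriate and recorded according to the MedDra dictionary". It gives no question and no times, and does not mention placebo recipients.

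The trial is single-blind. Section 5.7.4 states that "study clinicians and researchers will be aware of the drug allocation that was recommended by the adaptive trial algorithm". Section 5.4.3 states that "the participants will not be aware of whether they are taking placebo or baclofen tablets". No blinded adverse-event assessor is described.

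Section 8.3.6 tabulates adverse events for baclofen against placebo. Where useful, it adds time-to-event analyses to "display the difference in time to event curves between treatment groups (baclofen versus placebo) and baclofen dose group for comparative purpose".

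Other text is broader. The introduction to section 5.4 lists adverse effects among the measures taken before dosing and repeatedly afterwards, in participants given either treatment. Section 10.1.1 defines an adverse event without regard to cause, 10.1.3 says "All adverse events should be reported", and 10.1.4 has non-serious events recorded whether or not they were expected. Section 5.5 has every participant telephoned the next day about adverse events.

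**The concern.** A fair comparison of adverse events needs both arms to be asked in the same way. Nausea, headache and dizziness are symptoms that often enter the record only if someone asks. Section 5.7.1 lists dizziness and headache among baclofen's main adverse effects, and 7.1.1 reports dizziness and nausea in the investigators' earlier study. If the instruction is to look for effects of one arm's drug, as judged appropriate, and those judging know the arm and dose, then asking may differ by arm or by dose. Part of any difference in the 8.3.6 table would then reflect the asking.

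Timing is a second issue. A time-to-event curve for symptoms depends on when people were asked. Without fixed elicitation times, the recorded onset partly follows staff behaviour, even if staff are entirely even-handed.

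At stake is the descriptive tolerability comparison. Section 2.10 includes placebo partly to control for expectation effects. Unscripted asking by unblinded staff would let staff expectation back into this one comparison.

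**Working it through.** **1. The passages side by side**

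| Question | 5.4.12 | Elsewhere |
|---|---|---|
| Which events? | Side effects of baclofen | All adverse events, any cause (10.1.1, 10.1.3, 10.1.4) |
| Which arm? | Placebo not mentioned | Both arms (5.4, 5.4.3, 5.5, 5.4.15) |
| When? | As appropriate | Before dosing and at intervals after (5.4); no adverse-event row in the 4.3.2 grid; one tick for the whole visit in 5.6 |
| What is asked? | Not stated | Not stated, including for the next-day call (5.5) |
| Does the asker know the arm? | – | Yes (5.7.4) |

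The broader sections settle which events count and that both arms are covered. None says that participants are asked the same thing at the same times. The 4.3.2 grid does fix times for NEWS2, GCS, SHAS, DEQ, VAS and COWS. (The schematics in 4.3 could not be read in the text available; the key to 4.3.1 does not list adverse events.)

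**2. What the gap could do: an illustration**

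The plan gives no adverse-event rates and no power calculation (8.1), so it has no figure to reproduce. The only input from the documents is the maximum arm sizes, 48 and 16 (6.2). The true rates and detection probabilities are assumptions.

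- Observed rate = true rate × detection probability.
- Spurious difference = true rate × (detection on baclofen − detection on placebo), with the true rate p the same in both arms.
- 95% half-width for a difference = 1.96 × √[p(1 − p)(1/48 + 1/16)], evaluated at the common true rate. Here 1/48 + 1/16 = 1/12.

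| True rate, both arms | Observed, baclofen (90% detected) | Observed, placebo (70% / 50% detected) | Spurious difference, points | 95% half-width, points |
|---|---|---|---|---|
| 20% | 18% | 14% / 10% | 4 / 8 | 22.6 |
| 30% | 27% | 21% / 15% | 6 / 12 | 25.9 |
| 50% | 45% | 35% / 25% | 10 / 20 | 28.3 |

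The spurious risk ratio is 0.9/0.7 = 1.29 or 0.9/0.5 = 1.80, whatever the true rate. With 90% detection in both arms the difference is 0 and the ratio 1.0.

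In counts, at a 30% true rate, equal detection would record 16 × 0.27 = 4.3 placebo participants. Unequal detection records 16 × 0.21 = 3.4 or 16 × 0.15 = 2.4. The artefact is about one or two placebo participants.

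At the minimum numbers in 4.4.2 (30 on baclofen, 10 on placebo) the half-widths are wider: 28.6, 32.8 and 35.8 points.

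**The case against.** The strongest reply is that the plan, read as a whole, is arm-neutral. Section 5.4 already has adverse effects taken repeatedly around dosing. Section 5.4.3 monitors effects of either treatment for up to 5 hours, 5.4.15 keeps everyone under supervision for that time, 5.4.14 asks every participant about the experience, and section 10 requires all events. This stands in part. It rules out reading 5.4.12 as the only visit-day rule, and no passage says that placebo participants are assessed less. It does not supply a common question or fixed times.

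Sedation is largely protected. The SHAS has sedation items (2.6.2), is self-rated by blinded participants at fixed times in both arms, and is compared with placebo at each dose (3.4.4). The exposure lies mainly in minor symptoms outside the timed scales.

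Three stronger inferences are tempting and are not supported:

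- **That the comparison is biased.** Unequal asking is possible under the text but not stated in it. That staff would probe hardest at high doses is conjecture.
- **That staff are told to expect harm on baclofen.** Section 10.1.2 says "Most adverse events and adverse drug reactions that occur in this study, whether they are serious or not, will be expected treatment-related toxicities", but this is guidance on causality and refers to the study drugs in general. It does not direct a search in one arm.
- **That escalation is distorted.** The model uses the presence or absence of a dose-limiting toxicity (8.3.2). The criteria in 3.4.2 are thresholds on NEWS2, respiration, GCS, QTc and intervention level. Section 8.3.2 does mention tolerability and lets the Dose Setting Committee over-rule the model, so an indirect route exists. Nothing feeds the baclofen-versus-placebo adverse-event table into dosing.

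Finally, 8.1 plans no formal testing, and every illustrated artefact is smaller than the sampling half-width at the same true rate. That lowers the priority. It does not remove the point, because systematic error does not appear in an interval and does not shrink as participants are added.

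**Conclusion.** The point holds in a limited form. Section 5.4.12 is narrower than section 5.4 and section 10. With unblinded staff and no standard question, the adverse-event table and any time-to-event curves in 8.3.6 are open to detection bias, more plausibly towards extra events recorded on baclofen. The reach is a descriptive comparison, chiefly of minor symptoms. The protocol-timed safety measures, the self-rated scales and, directly, the dose-limiting toxicity model are outside it.

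The size cannot be derived from the documents. The 4 to 20 point range rests wholly on the assumed true rates (20% to 50%, equal in both arms) and detection (90% against 70% to 50%). It shows what unequal asking could do and does not estimate what will happen. This is a cheap improvement that makes the comparison easier to defend.

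**What to change.** - Reword 5.4.12 to cover all adverse events in both arms, consistent with 5.4 and section 10.
- Put the same scripted, non-leading open question to every participant at baseline, at 60, 120, 180, 240 and 300 minutes, and at the follow-up call. The baseline answer separates symptoms already present from new ones.
- Add an adverse-event row to the 4.3.2 grid at those times.
- Base the 8.3.6 comparison on these responses and list other staff-noted events separately.
- State beside the table that staff knew the allocation. A script equalises the asking but does not blind the person who records the answer.

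An open question is preferable to a repeated symptom checklist. A list made up largely of baclofen's known effects would cue them and add burden, which 5.6.1 tries to limit.

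Cost: protocol wording, one grid row, and about a minute per contact (an estimate). Six visit time-points plus the call make 7 contacts, so about 7 minutes per participant and 7 × 64 = 448 minutes at full enrolment. No extra visits are needed. The downside is that more minor events will be recorded in both arms.

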### **5.4.13 Actigraphy**

The wrist worn-actigraphs administered at the screening visit will be checked and re-administered for return the following day.

### **5.4.14 Debrief**

Participants will be asked about their experience of the session; whether they could guess whether they had placebo or drug, whether they thought it was a low or a high dose, and whether at any time they liked the drug effects they encountered.

### **5.4.15 Discharge**

Participants will be required to remain under supervision for a period of 5 hours after they receive baclofen/placebo, and remain at the research facility until approved for discharge by the study physician. Staff will ensure that any adverse impacts etc have attenuated before the participant leaves. Study staff will remind participants of relevant study contact details, including a 24-hour mobile telephone number for the on-call study doctor.

Where possible, study staff will arrange for a taxi to take the participant home.

### **5.4.16 Emergency contact**

Provided by on-call study doctor via study mobile.

## **5.5 Follow-up**

Following completion of experimental study visits, participants will be telephoned the day after the visit to check for the following:

- adverse events

- complete sleep and restless legs questionnaire- Leeds Sleep Evaluation Questionnaire (LSEQ, (Parrott AC and Hindmarch I. 1980)
- arrange return of questionnaires and actigraph
- If the participant is still sedated during the call, a second follow up will occur later that day or the following day.

The questionnaires can be completed online, or returned along with the actiwatch in a stamped addressed envelope or via the clinical service.

Any incidental findings will be discussed with the individual and appropriate action taken which could include passing information to GP and/or clinical addiction team as required.

## 5.6 Schedule of events

Event	Screening	Enrolment	Experimental	Follow-up
GENERAL				
Consent & eligibility	x		x	
General health	x		x	x
Demographics	x			
CLINICAL ASSESSMENTS				
Structured clinical interview (MINI)	x			
Medical examination	x			
Vital statistics (height, weight)	x			
Vital signs (BP, HR, SpO 2 )	x		x	
Respiratory function	x		x	
Blood sampling (clinical)	(x)			
Urine screen (DOA & pregnancy)	x		x	
Breath alcohol	x		x	
Methadone administration			x	
Baclofen administration			x	
DRUG & ALCOHOL HISTORY				
MTD dose check	x		x	
TLFB (drug & alcohol use)	x			
FTND	x			
AUDIT	x			
ASSIST (shortened)	x			
SDS	x			
OCDUS-H	x			
RANDOMISATION				
Randomisation & Enrolment		x		
MOOD & PERSONALITY				
BDI	x			
STAI	x			
SSAI	x			
BIS	x			
UPPS-P	x			
PSQI	x			
ESS	x			
STATE MEASURES				
VAS drug effects (DEQ)			x	
VAS craving	x		x	
VAS anxiety			x	
COWS	x		x	
LSEQ, sleep quality			x	x
Adverse events			x	x
BLOOD MEASURES				
Growth hormone			x	
Baclofen/Methadone			x	
ACTIGRAPHY MEASURES				
Actigraphy	x	x	x	x

### **5.6.1 Protocol events flexibility**

Whilst we will endeavour to complete all the questionnaires and tasks as detailed in the protocol if at the experimental visits it seems that the burden is too great on the participants, we will minimise this by omitting any unnecessary questions, questionnaires or tasks from the protocol, whilst still maintaining sufficient data to meet criteria for an evaluable participant, following discussion within the team as to the best course of action.

### **5.7 Study medications**

Baclofen (generic) tablets are expected to be acceptable to participants and well tolerated. The placebo will be Vitamin D3 (generic) tablets which are not expected to result in any noticeable effects or mood changes and are expected to be very well tolerated. Vitamin D tablets provide a good visual match to the baclofen tablets. Participants will not be told that the placebo tablets contain vitamin D as this could also create expectation effects. Instead they will be told that these are 'dummy' pills, and we will check for vitamin D contraindications at screening.

Participants will be randomised to receive oral baclofen (acute dose of 10, 30, 60 or 90mg), or placebo (an equivalent number of Vitamin D tablets), in a 3:1 ratio in a single-blind design.

The dose will be recommended by the adaptive model algorithm. We will administer baclofen 10mg as 1 x 10mg tablets, 30mg as 3 x 10mg tablets, 60mg as 6 x 10mg tablets and 90mg as 9 x 10mg tablets. The placebo group will receive the same number of Vitamin D tablets, according to the model recommendation, up to a maximum of 6 tablets, assuming the dose per tablet is 20 micrograms (total dose 120 micrograms or 4800IU).

Example SmPC for Vitamin D (Desunin, colecalciferol 20 micrograms/800IU)

<https://www.medicines.org.uk/emc/medicine/27007#gref>

#### **5.7.1 Baclofen in licensed indication**

For baclofen, BNF recommended maximum dose is 100mg/d for licensed indication of spasticity. Example SmPCs for generic baclofen can be found here:

Accord UK Ltd (10mg tablets)

<https://www.medicines.org.uk/emc/product/5728/smpc>

Advanz Pharma (10mg tablets)

<https://www.medicines.org.uk/emc/product/11781/smpc>

Mylan (10mg tablets)

<https://www.medicines.org.uk/emc/product/2594/smpc>

Baclofen is the only selective GABA-B agonist licensed for human use. Originally developed as a potential anti-epileptic in the 1920s, it was found to have anti-spastic effects and is currently used for the treatment of spastic movement, especially in instances of spinal cord injury, spastic diplegia, multiple sclerosis, and amyotrophic lateral sclerosis. It is an orally active *g*-aminobutyric acid (GABA) derivative, p-

chlorophenyl-gamma aminobutyric acid. Its primary action as an antispasticity agent is via simulation of GABAB-receptors resulting in depression of monosynaptic and polysynaptic reflex transmission. Baclofen increases K+ conductance resulting in postsynaptic inhibition and reduces Ca2+ influx and the release probability of excitatory transmitters (glutamate and aspartate) causing presynaptic inhibition in the brain and spinal cord (Katzung, 2009). Baclofen also exerts an antinociceptive effect and may act at supraspinal sites producing CNS depression. Baclofen may also modulate dopamine release in the mesocorticolimbic system by targeting neurons in the ventral tegmental area (Cruz et al., 2004).

Over its many years of use, baclofen has proven to be a very safe drug with few side effects. The main adverse effects are somnolence, dizziness, muscle weakness, and headache. Baclofen has good absorption after oral administration (75%), with peak serum concentrations achieved in 2–4 h. It is weakly bound (30%) to plasma proteins, and is eliminated primarily via the kidneys, 85% as the unchanged parent compound, with an estimated elimination half-life of 3-4 hours. The therapeutic serum concentration for spasticity is 0.08 to 0.4 microgram/ml.

### **5.7.2 Additional Supporting Information for the dose of baclofen**

#### **5.7.2.1 Baclofen in Alcohol dependence**

Very high doses of baclofen have been reported for use in alcohol use disorder for some patients ( $\leq 300\text{mg/d}$ ), which is 10 times higher than that used in the initial RCT in this indication. Meta-analyses established an efficacy signal in alcoholism with  $\leq 60\text{mg/d}$  compared with higher doses. Baclofen doses below 30mg/d have not demonstrated efficacy in alcoholism. A temporary license was granted in France for this indication up to 80mg/d (see section 2). In addition, we have comparative data using acute doses up to 90mg in our healthy control and alcoholic cohort showing that doses up to and including 60mg in controls and up to 90mg in alcohol dependent individuals were well tolerated (Durant et al., 2018). NB Only 10mg doses are available in the UK, making planned dose escalations of 10, 30, 60 and 90mg those most practicable options.

We reviewed the trials of baclofen in alcoholism to determine how they evaluated side-effects and adverse events, as there is no universally accepted gold-standard assessment (Singh & Loke, 2012). A systematic review of trials of baclofen in alcoholism (Pierce et al., 2018) reported that 9 of the 13 published studies reported no serious adverse events with one study not describing any such data. Of the remaining, the study with the highest prevalence of adverse effects investigated the highest dose of baclofen (Reynaud et al., 2017); ( $< 180\text{mg/d}$ ). It reported that 20 baclofen and 26 placebo patients experienced 40 and 43 serious adverse events (e.g. hospitalisation for alcohol detoxification, fall, suicidal ideation, depression) but most (70%) were considered unrelated to study medication. The other 2 studies reported one medication related serious adverse event: hospitalization due to constipation (Beraha et al., 2016); ( $< 150\text{mg/d}$ ) and one overdose (related to medication), two hospitalisations due to suicidal ideation/intoxication (possibly medication related), and one death (30mg/d, provisionally assessed as unrelated to medication; (Morley et al., 2018)). In all the trials, common side effects reported included sleepiness/drowsiness, vertigo, fatigue, dry mouth, headache, sleep disorders, asthenia/muscle weakness, and dizziness and which were more likely to be observed following higher (ie  $> 100\text{mg/d}$ ) doses than will be used in our study (Pierce et al., 2018; Rose & Jones, 2018). In summary, whilst many

patients taking baclofen will incur side-effects these are generally benign and attenuate within first few days (or with slower titration/dose reductions); potentially more serious ones include seizures, respiratory depression with sleep apnoea, severe mood disorders, and mental confusion/delirium and potentially coma, particularly in case of intoxication with alcohol or other sedative drugs or after taking a baclofen overdose (de Beaurepaire et al., 2019).

We have been unable to find any reports that baclofen is hepatotoxic and baclofen has been proposed as ideal in alcoholism where liver impairment is common. The first RCT of baclofen in alcoholism was in patients with cirrhosis where liver function improved (G. Addolorato et al., 2007). A study in patients with Hepatitis C reported that baclofen was well tolerated and there were no differences between groups in rates of serious drug-related adverse effects and discontinuation (Hauser et al., 2017). Thus studies and reports from clinical populations suggest that baclofen is well tolerated in patients with chronic liver disease (de Beaurepaire et al., 2019). It is recommended that baclofen not be used in patients with hepatic encephalopathy or hepatorenal syndrome but these are extremely unlikely in those undergoing community opiate detoxification as they would not be healthy enough (Leggio & Lee, 2017; Thursz et al., 2018)

